5.5.7 Concomitant treatment

The investigator should instruct the patient to notify the study site about any new medications he/she takes after the patient was enrolled into the study. All medications, procedures and significant non-drug therapies (including physical therapy and blood transfusions) administered after the patient was enrolled into the study must be recorded on the Prior and Concomitant medications or Procedures and Significant Non Drug Therapy eCRF. The reason, name of the drug, procedure or non-drug therapy should be listed.

Guidelines for the use of specific medications are provided below:

Methotrexate

Patients taking MTX (up to 25 mg/week) must be on a stable dose for at least 4 weeks before randomization and maintained stable until Week 12, except if MTX-related adverse events develop.

Folic acid

Patients on MTX must be taking folic acid supplementation before randomization and during the trial to minimize the likelihood of MTX associated toxicity.

Leflunomide wash-out with cholestyramine

In case of leflunomide treatment, a drug wash-out of 8 weeks has to be performed; however, another wash-out procedure may be considered. Cholestyramine could be given orally to washout the drug at a dose of 8 g t.i.d. Cholestyramine reduced plasma levels of the active leflunomide metabolite by approximately 40% in 24 hours and by 49% to 65% in 48 hours in 3 healthy volunteers. The administration of cholestyramine is recommended in patients who require a drug elimination procedure. If a patient receives 8 g t.i.d. for 11 days he/she could be safely randomized 4 weeks after the beginning of the 11- day treatment period.

Systemic corticosteroids

Treatment with systemic corticosteroids is permitted up to a maximum daily dose of 10 mg prednisone equivalent and if the dose was stable within the 2 weeks preceding randomization.

Corticosteroid dose reductions below 10 mg prednisone equivalent are permitted after Week 12. although the corticosteroid dose should not be reduced by more than 1 mg prednisone equivalent every 4 weeks.

After Week 12, the dose and regimen of systemic corticosteroids may be modified as per investigator's judgment and patient need.

Any change in the dose of systemic corticosteroids during the trial must be recorded on the corresponding eCRF page.

Intra-articular corticosteroids are not permitted within the 4 weeks preceding randomization and up to Week 12. After Week 12, no more than 1 joint per 24-week period may be injected. No single injection should exceed 40 mg of triamcinolone (or equivalent) and the total dose of intra-articular corticosteroid may not exceed 80 mg of triamcinolone (or equivalent) during any 20-week period. Injection of intra-articular steroids is not permitted within 8 weeks prior to Week 20.

Non-steroidal anti-inflammatory drugs (NSAIDs) (including COX-1 or COX-2 inhibitors), low strength opioids and acetaminophen/paracetamol

Patients regularly using NSAIDs, low strength opioids, or paracetamol/acetaminophen should be on stable dose for at least 2 weeks before randomization to allow inclusion. They should remain on a stable dose in the study up to Week 4.

Changes in the NSAID intake will be captured by the patient in the patient diary and checked and be transferred into the eCRF at all scheduled study visits after week 4.

Patients taking low strength opioids or paracetamol/acetaminophen PRN within the 2 weeks before randomization can continue to do so in the study; however, they have to refrain from any intake during at least 24 hours before a visit with disease activity assessment.

After Week 12 assessments are completed, a change in the low strength opioids, or paracetamol/acetaminophen treatment regimen is permitted.

Any change of the low strength opioids, or paracetamol/acetaminophen treatment during the trial should be recorded on the appropriate Prior and Concomitant medication eCRF page.

5.5.8 Prohibited treatment

Use of the treatments displayed in Table 5-1 is NOT allowed after the start of the washout period unless otherwise specified below.

Live vaccines should not be given until 12 weeks after last study treatment administration.

Table 5-1	Prohibited treatment
i able 5- i	Prombiled freatment

Prohibited treatments	Washout period (before randomization)
Etanercept*	4 weeks
Infliximab*	8 weeks
Adalimumab, golimumab, certolizumab*	10 weeks
Unstable dose of MTX or sulfasalazine (until Week 12)	4 weeks
Other DMARD (except MTX or sulfasalazine)	4 weeks
Leflunomide	8 weeks
Leflunomide with cholestyramine washout	4 weeks
Systemic corticosteroids > 10 mg prednisone equivalent** (until Week 12)	2 weeks
Intra-articular steroids injections (until Week 12)	4 weeks
Any investigational treatment or participation in any interventional trial	4 weeks or 5 half-lives (whichever is longer)
Analgesics other than paracetamol/acetaminophen or low strength opioids PRN	4 weeks
Live vaccinations	6 weeks

^{*}These agents fall under the category of biologic immunomodulators and are prohibited medications. Administration of these agents requires study discontinuation (see Section 5.5.8).

5.5.9 Discontinuation of study treatment

Patients may voluntarily discontinue investigational treatment for any reason at any time.

Patients who prematurely discontinue the study should undergo an end of treatment visit (corresponds to the Week 20 visit and also return for the end of study visit at Week 24 (4 weeks after last study treatment (see Table 6-1). The final follow-up visit (Week 24) should be performed before any new treatment is initiated. Study treatment discontinuation must also be recorded in the eCRF and in the IRT.

For patients who are lost to follow-up (i.e., those patients whose status is unclear because they fail to appear for study visits without stating an intention to withdraw from the study), the investigator should show "due diligence" by documenting in the source documents steps taken to contact the patient, e.g., dates of telephone calls, registered letters, etc.

Patients who are prematurely withdrawn from the study will not be replaced.

^{**}See details about corticosteroid management in Section 5.5.7.

Discontinuation of study treatment

Study treatment must be discontinued if the investigator determines that continuation of study treatment would result in a significant safety risk for a patient. The following circumstances **require** study treatment discontinuation:

- Withdrawal of informed consent
- Emergence of the following AEs:
 - Any severe or serious adverse event that is not compatible with administration of study medication, including adverse events that require treatment with an unacceptable concomitant medication
 - Onset of lymphoproliferative disease or any malignancy, except for treated basal cell
 carcinoma, treated actinic keratoses, treated in situ carcinoma of the cervix or noninvasive malignant colon polyps which are being or have been removed
 - Life-threatening infection
 - Any laboratory abnormalities that in the judgment of the investigator are clinically significant and are deemed to place the patient at a safety risk for continuation in the study (A general guidance on clinically notable laboratory values is provided in Appendix 1).
- Pregnancy
- Use of any biologic immunomodulating agent except Secukinumab
- Any protocol deviation that results in a significant risk to the patient's safety

In addition to these requirements for study treatment discontinuation, the investigator should discontinue study treatment for a given patient if there is a lack of improvement or worsening of their symptoms, or if on balance, he/she thinks that continuation would be detrimental to the patient's well-being.

For patients who discontinue study treatment, a Dosage Administration Record eCRF should be completed, giving the date and primary reason for stopping study treatment.

The investigator must also contact the IRT to register the patient's discontinuation from study treatment.

5.5.10 Withdrawal of consent

Patients may voluntarily withdraw consent to participate in the study for any reason at any time.

Withdrawal of consent occurs only when a patient does not want to participate in the study anymore and does not want any further visits or assessments and does not want any further study related contacts and does not allow analysis of already obtained biologic material.

If a patient withdraws consent, the investigator must make every effort (e.g. telephone, e-mail, letter) to determine the primary reason for this decision and record this information. Investigational treatment must be discontinued and no further assessments conducted. All biological material that has not been analyzed at the time of withdrawal must not be used. Further attempts to contact the patient are not allowed unless safety findings require communicating or follow-up.

5.5.11 Loss to follow-up

For patients whose status is unclear because they fail to appear for study visits without stating an intention to withdraw, the investigator should show "due diligence" by contacting the patient, family or family physician as agreed in the informed consent and by documenting in the source documents steps taken to contact the patient, e.g. dates of telephone calls, registered letters, etc. A patient should not be formally considered lost to follow-up until his/her scheduled end of treatment visit would have occurred.

5.5.12 Emergency breaking of assigned treatment code

Emergency treatment code breaks should only be undertaken when it is essential to treat the patient safely and efficaciously. Most often, investigational treatment discontinuation and knowledge of the possible treatment assignments are sufficient to treat a study patient who presents with an emergency condition. Emergency treatment code breaks are performed using the IRT. When the investigator contacts the system to break a treatment code for a patient, he/she must provide the requested patient identifying information and confirm the necessity to break the treatment code for the patient. The investigator will then be able to unblind details of the investigational drug treatment for the specified patient in the IRT system.

It is the investigator's responsibility to ensure that there is a procedure in place to allow access to the IRT in case of emergency. The investigator will inform the patient how to contact his/her backup in cases of emergency when he/she is unavailable. The investigator will provide protocol number, investigational treatment name if available, patient number, and instructions for contacting the sponsor (or any entity to which it has delegated responsibility for emergency code breaks) to the patient in case an emergency treatment code break is required at a time when the investigator and backup are unavailable.

Study patient must be discontinued after emergency unblinding.

As per Novartis standard operating procedures (SOPs) it is one of the primary responsibilities of each investigator to be available in case of an urgent emergency unblinding for one of his/her patients.

5.5.13 Study completion and post-study treatment

A patient will be considered to have completed the study if he/she received a maximum of 20 weeks of study treatment and upon completion of the scheduled study assessments and procedures up to and including the follow up visit (Week 24).

Information on the patient's completion or discontinuation from the study and the reason for discontinuation of the study will be recorded on the appropriate Study Phase Completion eCRF page.

In any case, the investigator or site staff must contact the IRT as soon as possible to record the patient's study completion (Week 24) and/or discontinuation.

The investigator must provide follow-up medical care for all patients who are prematurely withdrawn from the study, or must refer them for appropriate ongoing care. This care may include initiating another treatment outside of the study as deemed appropriate by the investigator. This treatment may be any non-biologic DMARD. In case of a biologic treatment, a waiting period of 3 months before initiating the treatment is recommended.

5.5.14 Early study termination

The study can be terminated at any time for any reason by Novartis for any reason specified in the clinical trial study contract. Should this be necessary, the patient should be seen as soon as possible and treated for a prematurely withdrawn patient. The investigator may be informed of additional procedures to be followed in order to ensure that adequate consideration is given to the protection of the patient's interests. The sponsor will be responsible for informing the Institutional Review Board/Independent Ethics Committee (IRBs/IECs) of the early termination of the trial.

6 Visit schedule and assessments

Table 6-1 lists all of the assessments and indicates with an "x" when the Visits are performed.

For visits scheduled through Week 4, the study treatment should not be administered less than 7 days after the previous administration. For visits scheduled after Week 4, the study treatment should not be administered less than 14 days after the previous administration. At a minimum, patients will be contacted for safety evaluations during the 30 days following the end of treatment visit at Week 20, including a final contact at the 30-day point. Documentation of attempts to contact the patient should be recorded in the source documentation.

Subjects who prematurely discontinue should return for the End-of-treatment visit (corresponds to the week 20 visit) 4 weeks after the last study treatment administration, as well as return for the follow-up (week 24). If they refuse to return for these assessments or are unable to do so, every effort should be made to contact them or a knowledgeable informant by telephone to determine the reason.

Screening will be flexible (up to 10 weeks) in duration based on the time required to washout prior anti-rheumatic and other medications and will have a duration, during which time the patient will sign the informed consent form (ICF), be evaluated for eligibility and sufficient time is allowed for potential medication washout, in addition to all other assessments indicated in Table 6-1.

Screening will consist of 2 consecutive visits. During Screening Visit 1, initial assessments will be performed as outlined in Table 6-1. At that visit, the duration of the washout period will be determined and Screening Visit 2 will be performed as follows:

- If the washout period is ≤ 4 weeks the investigator should proceed directly to Screening Visit 2 on the same day and complete all assessments in the next 4 weeks prior to randomization.
- If the washout period is more than 4 weeks, the patient will be instructed to initiate the necessary washout regimen and return for Screening Visit 2 at 4 weeks prior to randomization.

The rationale is that in all cases Screening Visit 2 must occur within the 4 weeks prior to randomization and should ideally be performed no less than 2 weeks prior to randomization to allocate time for laboratory analyses and shipment of medication.

All patients evaluated at Screening Visit 1 and 2 for eligibility should not be screen failed on the basis of a medication requiring washout, unless the patient will be unable to complete the washout in the appropriate time frame before randomization.

Table 6-1 Assessment schedule

	Scree	ening ¹																						
	Screening Visit 1	Screening Visit 2	Treatment 1									Treatment 2					Follow Up							
Week	-10 to -4	-4 to -2	BSL	1	2	3	4	5	6	7	8	12	16	17	18	19	20	F24						
Obtain informed consent	Х																							
Optional Site visit						X		х		Х				x	Х	Х								
Inclusion/Exclusion criteria ²	Х	Х	Х																					
Relevant medical history/ current medical condition	Х	Х	х																					
Prior medication	Х	Х	Х																					
AS assessment ³	Х																							
Demography	Х																							
Cardiovascular medical history		Х																						
Smoking history		Х																						
ECG⁴		X										Χ												
Physical exam ⁴		Χ	Х		Х		Х		Х		Χ	Х	Χ				Χ	X						
Height, weight		Χ																						
Vital signs	Х	Х	Х		Х		Χ		Х		Χ	Х	Х				Χ	X						

	Scree	ening ¹																
	Screening Visit 1	Screening Visit 2		Treatment 1 Treatment 2							Follow Up							
Week	-10 to -4	-4 to -2	BSL	1	2	3	4	5	6	7	8	12	16	17	18	19	20	F24
PPD skin test ⁵ or QuantiFERON TB- Gold test		Х																
Chest X-ray or MRI ⁶		Х																
Hematology, blood chemistry, urinalysis		Х	х		х		Х				х	х	х				Х	Х
Serum pregnancy test		Х																
Urine pregnancy test			Х				Х				Х	Х					Х	Х
Randomization			Х															
Administration of s.c. study treatment via PFS			х	Х	х	х	х	Х	Х	Х	х	х	х	х	Х	Х	Х	
Concomitant medication/ non- drug therapy	Х		•			•	•	•	•	Upda	ate as n	ecessar	ту	•	•	•		•

	Scree	ning¹																
	Screening Visit 1	Screening Visit 2		Treatment 1									Treatment 2					Follow Up
Week	-10 to -4	-4 to -2	BSL	1	2	3	4	5	6	7	8	12	16	17	18	19	20	F24
Adverse events/SAEs (if applicable, including injection site reactions) ⁷	X																	
NSAID intake reported in eCRF		Χ	Х	Х	Х	Х	Х											X
Provide NSAID Diary to patient and instruct patient							Х				Х	х	Х					
NSAID intake captured in patient diary								х	х	Х	Х	х	Х	х	Х	х	Х	
Check NSAID diary									Х		Х	Х	Χ				Χ	
Patient's global assessment of disease activity (VAS)			x	х	X		x		x		X	X	X				X	х
Patient's assessment of back pain intensity (VAS)			х	х	х		х		Х		Х	х	Х				Х	х
BASFI			Х	Х	Х		Х		Х		Х	Х	Х				Х	Х

	Scree	ning ¹																
	Screening Visit 1	Screening Visit 2		Treatment 1										Follow Up				
Week	-10 to -4	-4 to -2	BSL	1	2	3	4	5	6	7	8	12	16	17	18	19	20	F24
BASDAI			Х	Х	Х		Х		Х		Х	Х	Х				Х	Х
Spinal mobility (BASMI Linear + chest expansion)			х		Х		х				х	х	х				Х	
SF-36			Х				Х					Х					Х	
ASAS Health Index			Х				Х					Х					Х	
Erythrocyte Sedimentation Rate (ESR)		Х	х		Х		х				Х	х	х				Х	х
High sensitivity C-reactive protein (hsCRP)		Х	х		Х		Х				х	х	х				Х	х
HLA-B27			Х															

¹ If the patient's washout period ≤ 4 weeks, Screening visit 1 (SV1) and Screening visit 2 (SV2) can be performed on the same day.

² Eligibility and relevant medical history assessments are conducted at SV1, SV2 and Baseline (BSL) / Day 1'. The data for all three visits should be recorded on the corresponding eCRFs available at SV1.

³ The following eCRFs are to be completed: AS Disease background eCRF, Modified New York criteria for AS eCRF

⁴ These assessments are source documentation only and will not be entered into the eCRF.

⁵ The PPD skin test can be performed at any time during the Screening period, but it must be read within 72 hours and before randomization.

	Scree	ening ¹																
	Screening Visit 1	Screening Visit 2					Treat	tment	:1					Tre	eatment	2		Follow Up
Week	-10 to -4	-4 to -2	BSL	1	2	3	4	5	6	7	8	12	16	17	18	19	20	F24

⁶ A chest X-ray or MRI is required if it was not performed and evaluated within 3 months prior to Screening. The X-ray should be performed after it is certain the patient meets inclusion/exclusion criteria in order to minimize unnecessary exposure to radiation. The X-ray may be replaced by an MRI assessment.

⁷ AEs/SAEs occurring after the patient has signed the informed consent must be captured on the appropriate eCRF page. SAEs must be recorded from signing of informed consent, AEs must be captured from the BSL visit on.

^{*} For all patients who discontinue or withdraw from the study, the investigator should ensure that the patient completes an end of treatment visit.

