- 11. Patients who have taken more than two anti-TNFα agents
- 12. Previous treatment with any cell-depleting therapies including but not limited to anti-CD20 or investigational agents (e.g., CAMPATH, anti-CD4, anti-CD5, anti-CD3, anti-CD19)
- 13. Pregnant or nursing (lactating) women, where pregnancy is defined as the state of a female after conception and until the termination of gestation, confirmed by a positive human chorionic gonadotropin (hCG) laboratory test
- 14. Women of child-bearing potential, defined as all women physiologically capable of becoming pregnant, unless they are using effective methods of contraception during entire study or longer if required by locally approved prescribing information (e.g. 20 weeks in EU). Effective contraception methods include:
 - Total abstinence, when this is in line with the preferred and usual lifestyle of the patient. Periodic abstinence (e.g., calendar, ovulation, symptothermal, post-ovulation methods) and withdrawal are not acceptable methods of contraception
 - Female sterilization (have had surgical bilateral oophorectomy with or without hysterectomy) or tubal ligation at least six weeks before taking study treatment. In case of oophorectomy alone, only when the reproductive status of the woman has been confirmed by follow up hormone level assessment
 - Male sterilization (at least 6 months prior to screening). For female patients on the study, the vasectomized male partner should be the sole partner for that patient
 - Barrier methods of contraception: Condom or Occlusive cap (diaphragm or cervical/vault caps) with spermicidal foam/gel/film/cream/vaginal suppository
 - Use of oral, injected or implanted hormonal methods of contraception or other forms of hormonal contraception that have comparable efficacy (failure rate <1%), for example hormone vaginal ring or transdermal hormone contraception
 - Placement of an intrauterine device or intrauterine system

In case of use of oral contraception, women should have been stable on the same pill for a minimum of 3 months before taking study treatment.

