5.2 Treatment arms

Patients will be assigned to one of the following three treatment arms in a ratio of 1:1:1.

- **Group 1:** Secukinumab 150 mg s.c. at Week 0, 1, 2, 3, 4, 8, 12, 16 and 20; Placebo injections at Week 5, 6, 7 and 17, 18, 19 to maintain the blind for the initial treatment assignment
- **Group 2:** Placebo at Weeks 0, 1, 2, 3 followed by Secukinumab 150 mg s.c. at Week 4, 5, 6, 7, 8, 12, 16 and 20 with Placebo at Week 17, 18, 19 to maintain the blind for the initial treatment assignment
- **Group 3:** Placebo at Weeks 0, 1, 2, 3, 4, 5, 6, 7, 8 and 12. From Week 16, patients will be switched to receive Secukinumab 150 mg s.c. at Week 16, 17, 18, 19, and 20

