6.5 Safety

- QuantiFERON TB-Gold test or PPD skin test
- Chest X-ray or MRI
- Physical examination
- Vital signs
- Height and weight
- Laboratory evaluations
- Pregnancy and assessment of fertility
- Local tolerability (injection site reactions)
- Tolerability of Secukinumab

All blood draws and safety assessments should be done prior to study treatment administration. Appropriate safety assessments (e.g. evaluation of AEs and SAEs including injection site reactions) should be repeated after the dose is administered.

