6.5.8 Pregnancy and assessments of fertility

All pre-menopausal women who are not surgically sterile will have a serum β-hCG test (serum pregnancy test) performed at the second Screening visit and local urine pregnancy tests as indicated in Table 6-1.

A positive urine pregnancy test requires immediate interruption of study drug until serum βhCG is performed and found to be negative.

6.5.9 **Local tolerability (Injection site reactions)**

The local tolerability at the site of s.c. injection of the study treatment will be assessed in case of any local reaction, until this has disappeared.

The assessment of pain, redness, swelling, induration, hemorrhage and itching will be performed by a physician and will be recorded on the Adverse Events eCRF, including the severity (mild, moderate, severe) and the duration.

Tolerability of Secukinumab 6.5.10

Tolerability will be assessed by adverse events, laboratory values and injection site reaction.

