9.7 Sample size calculation

All sample size and power considerations are performed using EAST 6.

The sample size was calculated based on the phase III results of the MEASURE2 study, which used the same dose and loading regimen as will be applied in this trial. Under the assumption of 56.9% ASAS20 responders in the Secukinumab (delayed tapering) group and 27.0% in the placebo group, a sample size of 62 patients per group is required to have 90% power to show superiority of Secukinumab over placebo at a two sided $\alpha=5\%$.

For the comparison of the the early tapering group at week 16 vs. placebo, the same treatment effect is expected, leading to the same sample size. To compensate for some dropout and other protocol deviations, the sample size will be increased to 68 per arm. The total sample size of this trial will thus be 204. At the time of writing this amendment, about 190 patients have been recruited into this trial and it seems unlikely that a sample > 200 can be recruited within reasonable time. With this sample size, the (newly introduced) comparison of pooled

Secukinumab groups vs. placebo, the trial would still have almost 80 % (78%) power if the placebo response was somewhat higher (35%) than originally assumed...

Other secondary endpoints

It will be assumed that the amount of NSAID reduction observed in the etanercept SPARSE trial (Dougados et al. 2014), of 63.9 vs. baseline (etanercept) and 36.6 for placebo, with an estimated standard deviation of 40 will be seen in this trial for both Secukinumab groups versus placebo. Based on this assumption both secukinmab groups will have >90% power to show superiority over placebo for NSAID reduction.

For the total BASDAI parameter, 62 patients per treatment group should yield a power of approximately 91%, assuming a a treatment difference of 1.8 with a standard deviation of 2.8 (van der Heijde 2006). For SF-36 PCS, 62 patients per treatment group yield a power of approximately 87.5%, assuming mean change of 6.9 on both Secukinumab regimen and mean change of 1.6 on placebo with common standard deviation of 8.7 (Davis 2007).

10 Ethical considerations

Study documentation, record keeping and retention of documents

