10.2 Informed consent procedures

Eligible patients may only be included in the study after providing written (witnessed, where required by law or regulation), IRB/IEC-approved informed consent. Informed consent must be obtained before conducting any study-specific procedures (i.e. all of the procedures described in the protocol). The process of obtaining informed consent should be documented in the patient source documents.

Novartis will provide to investigators in a separate document an informed consent form that complies with the ICH GCP guideline and regulatory requirements and is considered appropriate for this study.

Women of child bearing potential should be informed that taking the study treatment may involve unknown risks to the fetus if pregnancy were to occur during the study and agree that in order to participate in the study they must adhere to the contraception requirement for the duration of the study or longer if required by locally approved prescribing information (e.g. 20 weeks in EU). If there is any question that the patient will not reliably comply, they should not be entered in the study.

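### Table 6-1 has no urine pregnancy test at Week 16, so the placebo arm takes its first secukinumab dose on a 4-week-old test (a minor schedule gap)

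*Protocol*

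**What the plan says.** Protocol Table 6-1 schedules a serum pregnancy test at Screening Visit 2. The row "Urine pregnancy test" is then marked at baseline, Weeks 4, 8, 12 and 20, and the Week 24 follow-up. Its Week 16 cell is empty. Week 16 is otherwise a full site visit, with physical examination, blood tests, urinalysis and dosing.

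No other text supplies a Week 16 test. Protocol 6.5.8 asks for "local urine pregnancy tests as indicated in Table 6-1" and so defers to the table. Protocol 7.5 says that pre-menopausal women will have a urine test but names no visit. SAP 2.8.4.3 only summarises the results by visit.

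Under Protocol 5.2, the delayed-tapering arm first receives secukinumab at Week 0 and the early-tapering arm at Week 4. For the placebo arm: "From Week 16, patients will be switched to receive Secukinumab 150 mg s.c. at Week 16, 17, 18, 19, and 20".

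Three further statements bear on the point:
- Protocol 6.5.8: "A positive urine pregnancy test requires immediate interruption of study drug".
- Protocol 6.5: "All blood draws and safety assessments should be done prior to study treatment administration".
- Protocol 10.2: women are to be told that "taking the study treatment may involve unknown risks to the fetus if pregnancy were to occur during the study".

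**The concern.** Two of the three arms have a pregnancy test on the day they first receive active drug. The third does not, and the one stretch where urine tests are 8 rather than 4 weeks apart covers its switch from placebo to secukinumab.

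What is at stake is the safety of a possible fetus. The protocol warns of unknown fetal risk and stops study drug on a positive urine test. If a woman in the placebo arm conceived after the Week 12 test could have detected it, and the pregnancy was detectable by Week 16, a pre-dose test that day would prevent her first secukinumab dose. Under the present schedule, the next planned test is at Week 20. No efficacy estimate or error rate is affected.

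**Working it through.** The plan gives no figure of its own on this point, so the check is a reading of the schedule followed by a rough estimate of yield.

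**1. Is the Week 16 cell really empty?** The header row and the urine-test row of Table 6-1 each split into 19 cells, so marks can be matched to visits. The urine-test marks fall at baseline, 4, 8, 12, 20 and F24. In the same part of the table, the haematology/chemistry/urinalysis row and the dosing row, also 19 cells each, do carry a Week 16 mark. A cell lost in text extraction is therefore unlikely.

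**2. Age of the latest scheduled urine test at the first secukinumab dose**
- Delayed tapering: 0 − 0 = 0 weeks
- Early tapering: 4 − 4 = 0 weeks
- Placebo: 16 − 12 = 4 weeks

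**3. Intervals between urine tests**
- As planned: 4 − 0, 8 − 4, 12 − 8, 20 − 12 and 24 − 20 give 4, 4, 4, 8 and 4 weeks.
- With a Week 16 test: six intervals of 4 weeks.

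**4. Conceptions that a Week 16 test would newly detect.** Let L be the weeks from conception to a positive urine test (not given in the documents). The Week 12 test finds conceptions before week 12 − L, and a Week 16 test finds those before week 16 − L. The added window is (16 − L) − (12 − L) = 4 weeks, whatever L is. Conceptions in the last L weeks before Week 16 would still be missed.

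**5. Expected number newly caught in the placebo arm**
- Placebo patients: 190 / 3 = 63.3 (total from Protocol section 4, ratio from 5.2).
- Women able to become pregnant, assumed 15-35%: 63.3 × 0.15 = 9.5 to 63.3 × 0.35 = 22.2.
- Contraceptive failure, assumed 1% a year. Protocol 4.2 (exclusion criterion 14) gives below 1% for hormonal methods without a time unit, and no rate for the barrier methods it also allows.
- Expected number = women × annual rate × 4/52:
  - low: 9.5 × 0.01 × 4/52 = 0.0073
  - high: 22.2 × 0.01 × 4/52 = 0.0171
- Chance of at least one: 1 − exp(−0.0073) = 0.7% to 1 − exp(−0.0171) = 1.7%.

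**6. Sensitivity.** The expected number is proportional to the failure rate. Ten times the assumed rate would give 0.073 to 0.171, still well below one.

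**7. Patient base.** Protocol 9.7 states that, at the time of the amendment, "about 190 patients have been recruited into this trial", and the amended target is also about 190. Only placebo patients who had not yet reached Week 16 could benefit. The figure of 63.3 is therefore an upper limit on the base, and the yield falls in proportion to the share already past that visit.

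**The case against.** The strongest reply is that nothing is breached. No section ties a pregnancy test to a first active dose, and the baseline and Week 4 tests may simply reflect a roughly 4-weekly rhythm. That stands. A reader might infer a contradiction or a broken safety rule from the empty cell, but the documents support only a gap in the schedule.

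A reader might also infer that the placebo arm alone takes a whole loading course between tests. It does not. Every arm receives four active doses from its first dose until its next test: Weeks 0-3, Weeks 4-7 and Weeks 16-19. Active doses without a same-day test are routine at Weeks 1-3 and 5-7, and both secukinumab arms are also dosed at Week 16 on the Week 12 test. What sets the placebo arm apart is only the missing test on the day of first exposure.

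Existing safeguards are real: a serum test at screening, urine tests up to Week 12, mandatory contraception, counselling, and the rule that a positive test interrupts treatment. Unscheduled tests remain possible. Some pregnancies would already be known at the Week 16 visit, and pregnancy requires discontinuation under Protocol 5.5.9. The yield in the working counts these as benefit, so it is generous in that respect too.

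Finally, the change is not free of process. Protocol 11.1 requires a written, approved amendment. All of this lowers the severity. None of it fills the Week 16 cell or gives a reason for leaving it empty.

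**Conclusion.** The point holds as a minor schedule gap. The placebo arm starts secukinumab on a 4-week-old test while the other two arms start on a same-day test, and the single 8-week interval spans the switch. The table and the treatment-arm description establish this without any assumption.

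The size of the benefit does rest on assumptions, namely the share of women able to become pregnant and the annual contraceptive failure rate. With 15-35% and 1%, the expected number newly caught is about 0.007-0.017 if the whole placebo arm could benefit, and less for the patients who had not reached Week 16 when the amendment was written. A different failure rate moves the figure in proportion. The case for the change is its low cost and consistency across arms, not a large expected gain. Lowest severity: a cheap improvement.

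**What to change.** In Protocol Table 6-1, mark a urine pregnancy test at Week 16 for pre-menopausal women who are not surgically sterile, in all three arms. Testing every arm keeps the original assignment blind. Protocol 6.5 already places safety assessments before dosing, so the test would be pre-dose without further wording, and 6.5.8 would pick it up through its reference to the table. SAP 2.8.4.3 needs no change because it reports by visit.

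The cost is one strip per eligible woman at a visit where urinalysis is already done: 190 × 0.15 = 28.5 to 190 × 0.35 = 66.5, so about 29-67 strips at most under the same assumed 15-35%. An occasional false positive would hold a dose until serum hCG is back. The change must also go through a protocol amendment, so it is best carried with other edits.
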